Visit 2: Medication Start Visit: Qualifying subjects will return for a medication start visit and DEXA scan for body composition and estimation of daily caloric needs. Subjects will be trained in the use of a CGM system (Dexcom G4 Platinum). The monitor will be in real time unblinded mode throughout the uptitration portion of each study phase for safety purposes by guarding against hypoglycemia due to insulin sensitization and allowing informed insulin dose adjustment with assistance from study personnel if needed. Baseline insulin dosing totals and average blood glucose will be recorded by subjects 3 days prior to starting the study medication. Subjects will also complete hypoglycemia and sleep questionnaires to assess frequency and awareness of lows, sleep patterns and sleep adequacy. Medication will be dispensed by the UCH or CHCO pharmacy to blind subjects and study personnel. Subjects will uptitrate study medication as follows: BCQR (0.8 mg) or placebo- 1 pill QAM for one week, then 2 pills QAM for one week, then 4 pills QAM for the remainder of the 4 weeks. If an uptitration step is not tolerated, subjects will be returned to the last tolerated dose for a few days and uptitration will be attempted again. If again not tolerated, subjects will remain at the last tolerated dose as long as this is at least 1.6 mg QAM. If unable to reach minimum acceptable dose, subjects will be withdrawn from the study.

Visit 3: Pre-MMTT Visit: Subjects will return for provision of Activwatch and review of CGM data from the past 3 weeks. There will be continued data collection regarding glycemic control, variability, frequency of hypoglycemia, physical activity, and sleep duration and quality. Detailed 7-day sleep and insulin diaries will again be provided for the last week. Prior to each post-medication metabolic study day, subjects will also be provided with a 1-day standardized, macronutrient-controlled, weight maintenance diet (45% carbohydrate, 20% protein, 35% fat) with caloric content based on prior DEXA lean body mass and an activity factor as in our previous studies. Depending on scheduling conflicts and the ability to pick up study diet, study staff may provide participants with food recommendations to eat 1 day prior to MMTT with the same macronutrient distribution listed above.

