Data handling: Data will be examined for completeness and errors during data cleaning, in order to remove any spurious or incorrect data and complete any missing data in the database where possible. Protocol deviations will be reported to COMIRB and the study Safety Officer within 30 days of the deviation. Deviations from the original statistical analysis plan will be reported to COMIRB with the next continuing review and disclosed in any publication resulting from this study.

Assessment of Safety: Safety parameters will include monitoring of any adverse events (AEs) or serious adverse events (SAEs), including number of hypoglycemic episodes and percentage of time spent hypoglycemic during the last week of CGM data. Safety parameters will be obtained by questionnaire at each visit, and will include reports of any AEs or SAEs.

At each visit, study subjects will be asked if they have had any AE, including illness, injury or hospitalization since the last visit. If so, the onset date, resolution date, severity and outcome will be recorded. All AEs will be reviewed by the PIs and a determination of SAE or AE status will be made. All SAEs will be reported to the IRB, safety officer, and sponsor following regulations. Bromocriptine is less well studied in adolescents and therefore further assessment of Bromocriptine's hypotensive effect will be monitored at each visit for adolescents aged 12-17 via orthostatic measurements. Assessment of intercurrent illnesses will be made by asking study participants of any illnesses or symptoms they have had since the prior visit, onset date and resolution date, severity and outcome of the illness. Subjects with SAEs will be followed until resolution of the event. All other subjects with AEs will be followed until the end of the study.

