Study stopping and subject discontinuation criteria: The trial will be stopped if >2 subjects meet criteria for individual subject discontinuation [≥ 2 hypoglycemic events requiring assistance or diabetic ketoacidosis (DKA) during a study phase] or if >2 subjects experience a serious adverse event (SAE) possibly or probably related to the study drug. Subjects will be withdrawn if they are unable to tolerate the minimum acceptable dose of BCQR (1.6mg QD) or if they experience a predefined SAE [infection related to blood draw or IV placement; severe hypoglycemia during the MMTT (blood glucose < 45 mg/dl), more than one episode of severe hypoglycemia requiring assistance or DKA while on study drug or other severe reactions possibly or probably related to the study drug]. No further data will be collected from withdrawn subjects. As some withdrawals are accounted for in the recruitment plan, there will be no specific replacement of withdrawn subjects. SAEs will be followed until resolution. Otherwise, withdrawn subjects will follow up with their care providers.

E. Potential Scientific Problems:

Interpretation of results: Based on the basic and clinical literature for BCQR, we expect that BCQR will reduce HGP and lipolysis throughout the day, effectively improving insulin action and reducing glycemic variability, improving glucose tolerance and control as evidenced by lower CGM-glucose and glucose AUC during MMTT, and/or decreasing insulin dose. Any of these results would support the use of BCQR as adjunct therapy in T1D. In addition, the presumed mechanism of BCQR supports an expectation of decreased vascular stiffness and improved endothelial function. These results would further support use of BCQR in T1D, even independent of glycemic benefits, as CVD risk reduction is an important goal in T1D with long term benefits in health outcomes, quality of life, and lifetime medical costs. We further speculate that the effects on sympathetic activation and circadian rhythm may improve sleep quality (thus further improving insulin sensitivity), blood pressure, hypoglycemia awareness, and thus hypoglycemia frequency and/or severity.

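### Orthostatic readings taken only at visits may miss many adolescents withdrawn for hypotension, because titration falls between visits and withdrawal ends data collection

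*Combined protocol and SAP*

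**What the plan says.** All references are to the combined protocol and SAP.

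- **Purpose.** The Investigational product section and Assessment of Safety both add orthostatic readings for adolescents only, to assess a named side effect. The second gives the reason, that the drug is less well studied at this age: "further assessment of Bromocriptine's hypotensive effect will be monitored at each visit for adolescents aged 12-17 via orthostatic measurements".
- **Dosing.** Visit 2 sets 0.8 mg pills as "1 pill QAM for one week, then 2 pills QAM for one week, then 4 pills QAM for the remainder of the 4 weeks". After a failed retry, "subjects will remain at the last tolerated dose as long as this is at least 1.6 mg QAM". Below that, "If unable to reach minimum acceptable dose, subjects will be withdrawn from the study".
- **Visits.** Each phase has three numbered visits (2 to 4, then 5 to 7): medication start, a pre-MMTT visit that reviews three weeks of CGM data, and the MMTT. Under the combined option for Visits 1 to 3, the week 3 contact is a phone call. In phase 2, adolescents may have study drug mailed to them.
- **After withdrawal.** The BCQR intervention text and the discontinuation criteria both state: "No further data will be collected from withdrawn subjects". SAEs are followed to resolution. "Otherwise, withdrawn subjects will follow up with their care providers".
- **Adverse events.** Subjects are asked about them at each visit, and "the onset date, resolution date, severity and outcome will be recorded". For non-serious events, "All other subjects with AEs will be followed until the end of the study".
- **Analysis.** The Data Analysis Plan specifies no summary of the orthostatic readings.

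**The concern.** The readings exist to show how far BCQR lowers blood pressure in adolescents. An adolescent with a marked fall is among those most likely to fail a dose step, and the text describes no visit while the dose is being raised. If that adolescent cannot hold 1.6 mg, withdrawal can come before any on-drug reading, and the withdrawal rule then closes data collection. Whether a reading is missing would then depend on the effect being measured, and a summary of the remaining readings could look more reassuring than the experience of all adolescents dosed.

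The follow-up rules also disagree. For an adolescent withdrawn with non-serious hypotension, Assessment of Safety requires follow-up to study end, while the discontinuation criteria hand the subject back to usual care with no more data.

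**Working it through.** The plan states no figure to reproduce. The check sets dosing days against visit days and then bounds the size.

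**1. Timing.** Dose steps start on day 0 (0.8 mg), day 7 (1.6 mg) and day 14 (3.2 mg). The first described on-drug visit is at about day 21, which is 21 − 14 = 7 days after the last step. With combined visits it is at about day 28, or 28 − 14 = 14 days after.

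**2. When would failure at 1.6 mg lead to withdrawal?** Withdrawal day = 7 + a + f + b, where a is days to first intolerance, f is days stepped back and b is days to second intolerance. The protocol gives no values, so these are assumed: a and b each 1, 3 or 7, and f 2, 3 or 5, making 27 combinations.

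- Earliest: 7 + 1 + 2 + 1 = day 11. Latest: 7 + 7 + 5 + 7 = day 26.
- Before day 21: 22 of 27, with no on-drug reading.
- On or after day 21: 5 of 27 (days 22, 22, 23, 24 and 26). In all five, day 21 falls within the second attempt at 1.6 mg, so Visit 3 could give an informative reading.
- With combined visits, all 27 precede day 28.

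The 27 combinations are not equally likely, so 22 of 27 is not a probability. Failure at 0.8 mg would normally come earlier. Adolescents who tolerate 1.6 mg but not 3.2 mg stay in and are read, at the reduced dose.

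**3. Bounds on size.** Recruitment plans 100 eligible and 80 completing, half adolescent: 100 × 0.5 = 50 eligible, 80 × 0.5 = 40 completing, so 10 losses from all causes. Let k of these be withdrawn on BCQR for hypotension without a reading. In a crossover, anyone lost during first-period placebo or the washout never takes BCQR, so the number dosed with BCQR lies between 40 + k and 50. If no one else shows an orthostatic drop, visit readings give 0% for every k. Counting the withdrawals gives:

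| k | k/50 | k/(40 + k) |
|---|---|---|
| 0 | 0% | 0% |
| 1 | 2.0% | 2.4% |
| 2 | 4.0% | 4.8% |
| 5 | 10.0% | 11.1% |
| 10 | 20.0% | 20.0% |

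For scale, 0 drops in 40 completers has an exact 95% upper limit of 1 − 0.025^(1/40) = 8.8%. Three such withdrawals stay within it (at most 3/43 = 7.0%). Five exceed it (at least 5/50 = 10.0%). Four depend on the denominator (4/50 = 8.0%, 4/44 = 9.1%).

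**The case against.** The strongest points on the other side are these.

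- **The timeline figure is not available.** The surviving labels of Figure 6 include day 14. If that were a visit, the gap would shrink: in the grid above only 4 of 27 withdrawals fall before day 14 and 3 fall on it. This leaves some doubt. However, the text ties no visit to day 14, and three numbered visits per phase leave no obvious place for one.
- **No orthostatic summary is planned.** This stands. The bias is conditional on someone summarising the readings, and the plan does not commit to a biased analysis.
- **Symptomatic harm is still captured.** This stands in large part. A reader might infer that hypotension would go unrecorded, but subjects are asked about adverse events at each visit and SAEs are followed. What can be lost is the measured blood pressure and its link to the dose change.
- **Silence about the reason is not a ban.** This is also fair. A reason noted when withdrawal is decided is not further data, and the protocol text is not a case report form. By itself this is only missing detail.
- **The specific withdrawal rule may override the general follow-up rule.** That is one possible reading, but the text does not say which prevails. Following the withdrawal rule as written drops follow-up of non-serious events.
- **A reading after stopping may be off drug.** This stands and shapes the fix.

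**Conclusion.** The point holds as a minor one. On the text, many adolescents leaving for hypotension before reaching 1.6 mg would have no on-drug orthostatic reading, and the two follow-up rules conflict for those with non-serious events. A summary of visit readings alone may understate the effect.

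A reader might infer that every adolescent who cannot reach 1.6 mg is missed. The documents do not support that, because slow failures can reach Visit 3. Those withdrawn may also have screening or start-visit readings, and placebo-phase readings if BCQR came second.

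The size is unknown. The range of 0 to 20 percentage points is a bound, not an estimate, and its upper end needs all 10 planned adolescent losses to be BCQR hypotension. It assumes that the recruitment figures split evenly by age and that no other adolescent shows a drop. If withdrawal is unrelated to blood pressure, no such bias is expected. No primary endpoint, power calculation or stopping rule is affected.

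**What to change.** 1. **BCQR intervention text and discontinuation criteria:** exempt two things from the no-further-data rule. One is follow-up of open adverse events, as Assessment of Safety already requires. The other is one orthostatic reading where feasible, preferably before the dose is reduced or stopped, with the time since the last dose.
2. **Visit 2 titration rules:** record the dose and the reason at each adolescent step-back or withdrawal.
3. **Data Analysis Plan:** add one safety table by treatment. The denominator is adolescents who took at least one dose in that phase. Show separately orthostatic drops at visits and step-backs or withdrawals for hypotension or syncope. List dizziness apart, with concurrent glucose, since hypoglycemia is also a listed effect of the drug. State the definition of a drop, taken from the procedure the protocol already cites.
4. Label any paired BCQR-placebo blood pressure difference as completers only.

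The cost is an occasional unscheduled contact and one extra table. On the recruitment figures that means at most about 10 adolescent withdrawals from all causes, plus an unknown number of step-backs. In-person readings will be harder for participants who live far away, hence the wording where feasible. No scheduled visit is added and power is unchanged.

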A. Outcome Measure(s):

Primary outcome measures are mean CGM glucose and insulin dose (SA#1), impact of age and BMI on response to therapy (SA#2) and improvement in brachial artery distensibility and RH-PAT (SA#3). Insulin dose was chosen as a clinical primary outcome because of the short treatment duration and to allow insulin dose adjustments as needed to avoid hypoglycemia. Secondary outcomes (see detailed methods below) include measures of (1) glycemic control (CGM parameters (SD, %hyperglycemic)); (2) baseline/postprandial metabolic labs [area under the curve (AUC) for MMTT glucose, insulin, NEFA, triglycerides, glucagon, and glucagon-like peptide1 (GLP1); (3) hypoglycemia frequency and awareness (CGM %hypoglycemic, hypoglycemia symptoms scores (Gold method, Clarke method, and the McAuley score⁶⁴⁻⁶⁷); (4) SNS activity (heart rate variability); (5) other metabolic markers (HDL, LDL); (6) circadian rhythm/sleep effects (sleep quality scores, measured sleep with actiwatch sleep monitor); (7) CVD measures (arterial stiffness by Dynapulse, endothelial function by EndoPAT, and blood pressure), and (8), blood storage for future inflammatory (IL-6, TNF- α , hsCRP, adiponectin), and vascular (endothelin 1, PAI-1, ICAM, renin, angiotensin, aldosterone) markers.

B. Description of Population to be Enrolled:

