Power and Sample Size: Power analysis and sample size are based on expected changes from the literature and from preliminary data for the primary outcomes for each aim. The sample size for the entire study was based on the power analysis for the subgroup analyses by age, in order to ensure adequate power to detect clinically meaningful treatment effects within each subgroup. In addition, we plan to examine the results by other characteristics (e.g. by obesity level, positive c-peptide status, etc.) in exploratory analyses which are not fully powered, but which may provide insight into heterogeneity in response to the therapy, thus guiding a future clinical trial if results of this study are positive. Desired α is set at 0.05. Since data used for this analysis are from within-subjects comparisons, repeated measures analysis will be used to compare outcome variables after each treatment (placebo, BCQR), adjusting for the randomization assignment of treatment order.

Assessment of Efficacy

The primary efficacy parameters will be change in insulin dose and CGM mean glucose on treatment versus placebo. Secondary efficacy measures will include change in post-MMT glucose and insulin AUC, and change in other CGM parameters (SD, %hyperglycemic, % hypoglycemic). Total daily basal and bolus insulin dose will be obtained at screening, and then at time zero for each medication phase. Insulin diaries will be obtained during the last week of each phase. Change in total, basal, and bolus insulin dose in units per day and total insulin in units per kg per day will be examined between medication phases to determine whether insulin requirements were lower at the end of the BCQR phase than the end of the placebo phase. Similarly, change in mean CGM glucose from the last 2 weeks of each medication phase will be examined to determine if overall mean glucose is decreased while on treatment versus placebo.

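### Any one of several results may count as support for BCQR, with a single alpha of 0.05 and no error control across the outcomes

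*Combined protocol and SAP*

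**What the plan says.** **Rule for reading the results.** Section IV.E, Interpretation of results, expects less glycemic variability and benefit in the form of "improving glucose tolerance and control as evidenced by lower CGM-glucose and glucose AUC during MMTT, and/or decreasing insulin dose". It then concludes: "Any of these results would support the use of BCQR as adjunct therapy in T1D". On lower vascular stiffness and better endothelial function it adds: "These results would further support use of BCQR in T1D, even independent of glycemic benefits". The primary hypothesis in the opening summary is also either/or: better glycemic control, lower insulin requirements, or both.

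**Error rate.** Section IV.F, Power and Sample Size, says "Desired α is set at 0.05". The Analysis Plan describes a paired t-test and a repeated measures regression for the outcomes. The only test level it gives is p<0.10 for the interaction screen. No adjustment, testing order or lead outcome is given anywhere.

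**Which outcomes are primary.**
- Section IV.A: "Primary outcome measures are mean CGM glucose and insulin dose (SA#1), impact of age and BMI on response to therapy (SA#2"), followed by brachial artery distensibility (BrachD) and RH-PAT for SA#3.
- Section IV.A, secondary group (7): "7) CVD measures (arterial stiffness by Dynapulse, endothelial function by EndoPAT, and blood pressure").
- Section IV.F, Assessment of Efficacy: "The primary efficacy parameters will be change in insulin dose and CGM mean glucose on treatment versus placebo".
- Section IV.F, SA3: BrachD and RH-PAT RHI are primary; AI and HRV are secondary.

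**Versions of insulin dose.** Assessment of Efficacy will examine "Change in total, basal, and bolus insulin dose in units per day and total insulin in units per kg per day", without naming the one that decides.

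**The concern.** When any one of several outcomes is enough, an inactive drug gets several chances to look active. The plan sets the level for one test and then allows a conclusion from whichever test succeeds. The conclusion concerns use of BCQR as adjunct therapy, so the error rate of the whole rule matters more than that of each component.

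The overlapping labels add to this. Endothelial function by EndoPAT is RHI, which is primary for SA#3 and also appears in a secondary group. Insulin dose has four versions. The plan promises to report and disclose deviations from the analysis plan, but a choice among options that the plan itself leaves open would not register as a deviation.

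**Working it through.** **1. Reproduce the plan's SA1 figures.** Inputs from section IV.F, SA1: SD of change 18.8 units/day and 10.03 mg/dl; n=80 overall and 40 per age group; 80% power. Normal approximation, paired data:

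detectable change = SD × (z(1−α/2) + z(0.80)) / √n, with 1.960 + 0.842 = 2.802 at α = 0.05.

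| Outcome | n | Computed | Plan |
|---|---|---|---|
| Insulin dose | 80 | 18.8 × 2.802/√80 = 5.89 | 5.9 |
| Insulin dose | 40 | 8.33 | 8.3 |
| CGM glucose | 80 | 10.03 × 2.802/√80 = 3.14 | 3.1 |
| CGM glucose | 40 | 4.44 | 4.4 |

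A one-sided 0.05 gives 5.23 and 2.79 at n=80, which does not match. Each SA1 outcome was therefore powered at the full two-sided 0.05.

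**2. Count the outcomes.** Two: the pair in Assessment of Efficacy. Four: variability, CGM glucose, mixed-meal glucose AUC and insulin dose in section IV.E (or the SA1 and SA3 primaries together). Six: those four plus vascular stiffness and endothelial function.

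**3. Chance of at least one false result if BCQR has no effect.** For m independent tests at two-sided 0.05 the chance is 1 − 0.95^m in either direction, and 1 − 0.975^m counting only the favourable direction. Correlated cases are from 1,000,000 simulated draws of equally correlated normal statistics. The correlations are assumptions, because the documents give none.

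| | m=2 | m=4 | m=6 |
|---|---|---|---|
| Either direction, independent | 9.8% | 18.5% | 26.5% |
| Either direction, correlation 0.5 | 9.0% | 15.6% | 20.8% |
| Either direction, correlation 0.9 | 7.0% | 9.4% | 10.9% |
| Favourable only, independent | 4.9% | 9.6% | 14.1% |
| Favourable only, correlation 0.5 | 4.5% | 7.8% | 10.4% |
| Favourable only, correlation 0.9 | 3.5% | 4.7% | 5.4% |

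The comparison for one test is 5% in either direction and 2.5% in the favourable direction. Age-group tests, interaction tests and the extra dose versions are not counted.

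**4. Cost of Holm on the SA1 pair.** Holm tests the smaller p-value at 0.025 and, if that succeeds, the other at 0.05. The worst case for either outcome is a test at 0.025. Detectable change at 80% power, noncentral t:

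| Outcome | n | α = 0.05 | α = 0.025 |
|---|---|---|---|
| Insulin dose, units/day | 80 | 5.96 | 6.59 |
| Insulin dose, units/day | 40 | 8.54 | 9.47 |
| CGM glucose, mg/dl | 80 | 3.18 | 3.51 |
| CGM glucose, mg/dl | 40 | 4.56 | 5.05 |

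The ratios are 6.59/5.96 = 1.11 and 3.51/3.18 = 1.10. By the plan's own normal approximation, worst-case power at n=80 falls from 80.2% to 71.4% for 5.9 units/day and from 78.9% to 70.0% for 3.1 mg/dl (69.9% and 68.4% by noncentral t). Restoring 80% for those effects in the worst case would take 97 and 100 completers.

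**The case against.** **Direction.** The strongest objection is that only a result in BCQR's favour can support BCQR. A reader might infer from the first row of the error table that a false claim is two to five times as likely as the stated alpha (9.8/5 = 1.95; 26.5/5 = 5.3). The documents do not support that. Those multiples need independent outcomes and count significant harm as support. Favourable results alone give 1.0 to 2.8 times 0.05 if independent, and 0.9 to 2.1 times at correlation 0.5. For the SA1 pair, a false favourable claim cannot exceed 2 × 2.5% = 5% under any correlation. This part of the objection stands. Multiples of 2.0 to 5.6 arise only against 2.5%, which is the per-test favourable rate and not the stated alpha.

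**Count.** Six is the widest reading. The text joins CGM glucose and mixed-meal AUC with an 'and', and all outcomes come from the same subjects. The Analysis Plan does not say that every outcome is tested at 0.05; for SA1 this is inferred from the power figures. These are fair cautions, so the size is given as a range.

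**Pilot status.** The design section calls the study a pilot, the closing section speaks of preliminary data, and the power section looks ahead to a future trial. That lowers the stakes. It does not remove the point: the study is formally powered at 0.05, and the sentence in section IV.E speaks of use as therapy.

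**Primary set.** A reader might infer that the primary set is wholly open. It is not. Primaries are assigned by aim, section IV.F repeats the SA3 pair, and the power calculation in units/day points to total daily dose. What remains is the overlap with secondary group (7) and the absence of an explicit lead dose version.

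**Conclusion.** The concern holds in a limited form. The plan states an any-one-suffices rule, powers each SA1 outcome at the full 0.05 and has no multiplicity control. For 2 to 6 outcomes at two-sided 0.05, the chance of at least one false significant result is up to 10% to 26% if independent and 9% to 21% at correlation 0.5. For results favouring BCQR it is about 5% to 14% and 4.5% to 10%, against a nominal 2.5% per test. At correlation 0.9 the favourable-only figure is only 3.5% to 5.4%.

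These figures rest on assumed equal correlations, on the count of outcomes, and on each outcome being tested at two-sided 0.05. A reader might also conclude that the vascular outcomes must lose primary status. That does not follow: they are declared and powered as primaries of a separate aim, and the problem is only that a vascular result alone may be read as support for use.

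**What to change.** 1. For SA1, name total daily insulin dose in units/day (the version that was powered) and CGM mean glucose as the two confirmatory outcomes, tested with Holm at an overall two-sided 0.05.
2. Limit the any-of-these-results sentence in section IV.E to that pair.
3. Label mixed-meal AUC, glycemic variability and the other dose versions (basal, bolus, units/kg) as secondary.
4. Keep BrachD and RHI as the SA3 primaries, take them out of secondary group (7) in section IV.A, and describe a vascular-only result as supportive, not as stand-alone support for use.
5. Update the SA1 detectable differences and power to the Holm level.

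**Cost.** This changes wording and power figures, with no change to visits or procedures. Detectable changes for the pair rise by about 10% in the worst case, and power for the stated n=80 effects falls to about 70% to 71% on the plan's own approximation. The loss is smaller if both outcomes respond. The n=40 figures matter too, because the sample size rests on the age groups and the adolescent cohort is conditional on adult safety. A vascular benefit without a glycemic or dose benefit could no longer carry the therapeutic conclusion alone.
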